5.2.5 Efficacy Analysis

5.2.5.1 Primary endpoint analysis

Primary efficacy analysis

Descriptive statistics for (i) raw values at each time point and (ii) change from baseline to each time point in FVC [% predicted] will be computed by treatment group for the ATS analysis dataset (Statistical tables 14.2.1.1.1 and 14.2.1.2.1). The time variation in FVC [% predicted] will be modelled using a linear mixed effect model with random intercept, with raw values at each time point (from Week 4 to Week 28 included) in FVC [% predicted] as dependent variable (outcome), and stratum, treatment, time (continuous variable calculated as the actual number of days since baseline) and treatment by time interaction as explanatory variables (Statistical table 14.2.1.3.1).

The following statistical hypotheses will be tested:

- H0: Absence of difference between the treatment groups.
- H1: A difference exists between the treatment groups.

Least square means for FVC [% predicted] at each time-point (Statistical table 14.2.1.3.1, Figure 14.2.1.1), estimate of slopes, together with their 2-sided 90 and 95% confidence intervals will be presented for both treatment groups.

The comparison of PRM-151 with placebo will be carried out by

1. computing the estimate (estimate statement from SAS Proc MIXED) of the between group difference in change from baseline at week 28,
2. computing the corresponding 90% confidence interval
3. computing the p-value of the difference estimate compared to 0.

Statistical significance will be determined using a 2-sided type-one error rate of 0.10.

The listing of the estimates of the random parameters will be provided (Listing 16.2.6.9.1)

Due to the number of sites planned to recruit and randomize patients in the study, it is expected that each site will include too few patients to allow the inclusion of study site as a covariate in the analysis.

Sensitivity efficacy analysis on the Full Analysis Set population

To assess the effect of including or excluding patient without any post-baseline efficacy measurement from the primary efficacy analysis population (ATS), the primary efficacy analysis described above will be repeated on the Full analysis set population (initially planned in the protocol as the primary efficacy population) and defined as all randomized patients having received at least one administration of the study medication with a baseline and at least one post-baseline assessment of FVC [% predicted] (primary efficacy criterion) available (Statistical tables 14.2.1.1.3, 14.2.1.2.3 and 14.2.1.3.3, Figure 14.2.1.3)

Sensitivity efficacy analysis on the ATS dataset

The primary efficacy analysis as described above will be repeated with addition of descriptive statistics by stratum, and of the treatment by stratum by time interaction, together with the three two by two interactions, terms in the analysis model (Statistical tables 14.2.2.1, 14.2.2.2, 14.2.2.3, Figure 14.2.2).

In case of a significant qualitative treatment by stratum by time interaction, the data will be carefully examined searching for a potential explanation and the conclusions of the primary efficacy analysis will have to be interpreted cautiously.

The primary efficacy analysis as described above will be repeated without adjusting on stratum in the analysis model (Statistical table 14.2.3).

Potential differences in treatment effect according to study site will be addressed by tabulating both raw values of FVC [% predicted] and change from baseline to each visit in FVC [% predicted] by site on the ATS (Statistical tables 14.2.4.1.1 and 14.2.4.2.18), but it is expected that due to the small number of patients within each site no precise estimates will be obtained for most of the sites.

Sensitivity efficacy analysis on the PP dataset

The primary efficacy analysis as described above will be repeated on the PP analysis data set (Statistical tables 14.2.1.1.2, 14.2.1.2.2 and 14.2.1.3.2, Figure 14.2.1.2).

Initially planned primary efficacy analysis (ATS and FAS)

The initially planned primary efficacy analysis will be computed on both the FAS and the ATS: Descriptive statistics for (i) raw values at baseline and week 28 and (ii) for change from baseline to Week 28 in FVC [% predicted] will be computed by treatment group. The mean change from baseline to Week 28 in FVC [% predicted] will be compared between treatment groups using an ANOVA model with treatment group and stratum as explanatory variables. This analysis will use Multiple Imputation relying on monotone regression methods (both efficacy variables including 6MWD, DLCO and other variables such as gender or age can be used in the imputation model) for missing data at week 28. Least square means for changes from baseline to Week 28 in FVC [% predicted], together with their 2-sided 90 and 95% confidence intervals will be presented for each treatment

groups (Statistical table 14.2.5.1.1 and 14.2.5.2.2). The mean difference between the two groups will also be presented with its 2-sided 90 and 95% confidence intervals.

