5.1.2 Significance testing and estimation

For the primary efficacy analysis (see Section 5.2.5.1), the overall type-one error rate will be set to 0.10 two sided. There will be one single primary efficacy analysis, from which the conclusions on efficacy will be drawn. Consequently, there is no issue of multiplicity of primary analyses and no need to adjust the significance level.

For secondary and exploratory endpoint analyses, 90% CIs will be computed. P-values will also be computed for key secondary efficacy endpoints. No adjustment of the type-one error rate will be conducted. As a consequence, the results of these tests will have to be interpreted bearing in mind the issue of multiplicity and the increased risk of erroneously obtaining statistically significant results.

For all fitted models (*i.e.*, Linear Models and Linear Mixed Models), the underlying model assumptions (e.g., homoscedasticity, linearity, independence) and the goodness of fit will be checked graphically.

Missing values will not be imputed for exploratory analyses. Consequently, for all models involving 'Time' effect, the 'Time' variable will be treated as a continuous variable. However, if the analysis of the residuals of a given model suggests departures from the underlying model assumptions, it will be re-fitted considering 'Time' as a categorical variable (8 modalities) in order to explore non-linear trend in response variable.

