5.2.5.3 Exploratory efficacy analyses

For all exploratory efficacy endpoints, the analyses will be based on observed data only *i.e.*, no data will be imputed.

EO1: To evaluate the efficacy and estimate the size of effect of PRM-151 relative to placebo in change from baseline to weeks 4, 8, 12, 16, 20, and 24 in FVC % predicted, FVC in ml and 6 minute walking distance, pooling subjects on a stable dose of pirfenidone or nintedanib with subjects not on other treatment for IPF and separately in subjects on a stable dose of pirfenidone or nintedanib and in subjects not on other treatments for IPF.

A model similar to that of the primary analysis (see section 5.2.5.1) but with the addition of random slopes will be used to evaluate on both the ATS and the PP data sets the efficacy and estimate, pooling subjects on a stable dose of pirfenidone or nintedanib with subjects not on other treatment for IPF and separately in subjects on a stable dose of pirfenidone or nintedanib and in subjects not on other treatments for IPF, the size of effect of PRM-151 relative to placebo in time variations in FVC [% predicted] (Statistical tables 14.2.13.1 to 14.2.14.2.2, Figures 14.2.10.1 to 14.2.11.2.2), FVC [ml] (Statistical tables 14.2.15.1 to 14.2.16.2.2, Figures 14.2.12.1 to 14.2.13.2.2) and 6MWD (Statistical tables 14.2.17.1 to 14.18.2.2, Figures 14.2.14.1 to 14.2.15.2.2). The individual slopes and intercepts will be listed (Listings 16.2.6.10 to 16.2.6.12). Statistical inference (90% CI and p-values) on the slope difference between treated and placebo groups will be reported.

EO2: To assess the impact of PRM-151 on disease related symptoms and quantitative imaging.

Mean change from Baseline to Week 28 in total lung volume and volume of parenchymal features (see section 8) on HRCT (in ml and % of total lung volume), representative of interstitial lung abnormalities (ILA) will be computed, comparing PRM151 vs. placebo (separately) in patients with SVC breathhold at CT scanning $\geq 90\%$ of SVC supine, with a similar approach to the one used

for the primary analysis (statistical tables 14.2.19.1.1.1 to 14.2.19.2.3.2, Figure 14.2.16.1.1 to 14.2.16.2.2).

For all categories of lung features (including PVV), the change from baseline to week 28 in volume of a given lung feature (both in ml as well as in % of total lung volume) will be computed in subjects treated with PRM-151 and placebo, depending on the completeness and usability of the obtained data.

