5.3 Statistical/Analytical issues

5.3.1 Adjustments for Covariates

All comparisons of change from baseline to a given visit between treatment groups performed using ANOVA models and pooling subjects on a stable dose of pirfenidone or nintedanib with subjects not on other treatment for IPF, are adjusted for stratification levels.

Analysis of time variation in a given variable using Linear Mixed Models and pooling subjects on a stable dose of pirfenidone or nintedanib with subjects not on other treatment for IPF, are all adjusted for baseline measurements of the response variable and stratification levels.

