5.3.5 Multiple Comparison/Multiplicity

There will be one single primary efficacy analysis, from which the conclusions on efficacy will be drawn. Consequently, there is no issue of multiplicity of primary analyses and no need to adjust the significance level.

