6.3 Changes in exploratory efficacy analyses

All exploratory efficacy analysis will be performed on both the ATS and the PP.

It was initially planned (EO1) to evaluate the efficacy and estimate the size of effect of PRM-151 relative to placebo in change from baseline to weeks 4, 8, 12, 16, 20, and 24 in FVC % predicted, FVC in ml and 6 minute walking distance using mixed models with random intercepts. To obtain a better description of individual variability, both random intercepts and random slopes will be used.

The following not initially planned exploratory analysis were added (see section 5.2.5.3 for details):

- To assess the use of quantitative imaging in IPF (E03)
- To explore the relationship between Anti-Pentraxin 2 antibodies (ADA) presence and level of FVC [% predicted] in time
- To explore PK/PD relationship.
- To explore relationship between Pentraxin-2 levels and ADA
- To explore acute exacerbations
- To explore time variations in FVC % predicted separately in patient (i) on stable dose of pirfenidone and (ii) on a stable dose of pirfenidone.

7 Software documentation

All summaries and statistical analyses will be generated using SAS version 9.4 or higher.

8 Derived data

Derived variable	Derivation algorithm
Change from baseline to visit V (continuous)	Change from baseline of variable $X = X_{(Visit V)} - X_{(Baseline)}$ 
 ○ Negative values indicate a decrease in X ○ Positive values indicate an increase in X

Percent change from baseline to visit V (continuous)	Percent change from baseline of variable X= $100 * [X_{(Visit V)} - X_{(Baseline)}] / X_{(Baseline)}$ 
 ○ Negative values indicate a decrease in X ○ Positive values indicate an increase in X
Treatment compliance	Continuous variable: The compliance C_i for patient i will be computed according to: $C_i = \frac{D_i^t * 100}{D_i^p}$ 
where D_i^p mg is the total amount (mg) of IP prescribed to patient i and D_i^t is the total amount (mg) of IP actually taken by the patient during the study i.e., before the end of study for patient i.

Treatment compliance (categorical)	Categorical variable with three modalities: 
 • $C_i < 80\%$ • $80\% \leq C_i < 120\%$ • $C_i \geq 120\%$

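### The primary model has a random intercept but no random slope, so its Week 28 test and 90% CI are valid only if FVC slopes do not vary between patients

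*SAP*

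**What the plan says.** SAP 5.2.5.1 fits the FVC % predicted values from Weeks 4 to 28 on stratum, treatment, time in days as a continuous variable, and treatment by time: "The time variation in FVC [% predicted] will be modelled using a linear mixed effect model with random intercept". The treatment comparison is made by "computing the estimate (estimate statement from SAS Proc MIXED) of the between group difference in change from baseline at week 28", with a 90% CI and a p-value judged at two-sided 0.10. No random slope, other covariance structure or empirical variance is specified for this model.

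For the same outcome, exploratory analysis EO1 (SAP 5.2.5.3) says: "A model similar to that of the primary analysis (see section 5.2.5.1) but with the addition of random slopes will be used". SAP 6.3 gives the reason: "To obtain a better description of individual variability, both random intercepts and random slopes will be used".

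SAP 5.1.2 plans graphical checks of model assumptions. If they fail, its only named remedy is to refit time "as a categorical variable (8 modalities) in order to explore non-linear trend in response variable". The protocol's ANOVA on Week 28 change is kept as a sensitivity analysis: "This analysis will use Multiple Imputation relying on monotone regression methods". SAP 5.3.5 nevertheless settles which result counts: "There will be one single primary efficacy analysis, from which the conclusions on efficacy will be drawn".

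**The concern.** With linear time and a treatment-by-time term, the difference in change at Week 28 is the difference in slopes multiplied by 28 weeks. A patient's random intercept cancels out of a slope; a patient's own rate of decline does not. The random-intercept model puts slope variation into the residual and treats it as independent visit-to-visit noise, averaged over seven visits. The standard error of the slope contrast is then too small.

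The stated aim is a reliable estimate of effect size (SAP 2.3.2). If slopes vary, the primary 90% CI is too narrow and the 0.10 test rejects too often. The primary analysis and EO1 could also disagree on the same data purely because of the covariance model.

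**Working it through.** **The plan's own sample size.** The expected placebo change is 0.75 × (−1.5) + 0.25 × (−3) = −1.875 and the expected PRM-151 change is 0.75, a difference of 2.625. With SD 5, 2:1 allocation, two-sided 0.10 and 80% power, the placebo arm needs 1.5 × 25 × (1.645 + 0.842)² / 2.625² = 33.7, so 34, and 102 in total. This matches SAP 2.3.2 (power 80.4% at 68 + 34). The sample size is not in dispute.

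**Set-up.** Scale time so that Week 28 = 1. The visits are t = 1/7, …, 1, and Sxx = Σ(t − mean)² = 28/49 = 0.571. The documents do not split the variance of 25 for the Week 28 change, so the split is an assumption. Let f be the share due to slopes:

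- slope variance: s_b² = 25f
- visit-noise variance: s_e² = 25(1 − f)/2, because the change contains two noisy measurements

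**Per-patient variance of the slope contrast.**

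- True: s_b² + s_e²/Sxx
- Reported by the random-intercept model: s_b²/6 + s_e²/Sxx. The within-patient residual mean square on 6 df is s_e² + s_b²·Sxx/6, which is then divided by Sxx.
- With r = reported SE / true SE, actual type I error = 2[1 − Φ(1.645 r)].

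Worked at f = 0.25: s_b² = 6.25 and s_e² = 9.375. True variance = 6.25 + 16.41 = 22.66; reported = 1.04 + 16.41 = 17.45; r = √(17.45/22.66) = 0.878; type I error 14.9%.

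| f | slope SD | noise SD | r | type I error, formula | simulated | 90% CI coverage |
|---|---|---|---|---|---|---|
| 0 | 0 | 3.54 | 1.000 | 10.0% | 10.0% | 90% |
| 0.05 | 1.12 | 3.45 | 0.976 | 10.8% | 11.5% | 89% |
| 0.10 | 1.58 | 3.35 | 0.952 | 11.7% | 12.2% | 88% |
| 0.25 | 2.50 | 3.06 | 0.878 | 14.9% | 14.3% | 85% |
| 0.46 | 3.39 | 2.60 | 0.767 | 20.7% | 20.5% | 79% |
| 0.52 | 3.61 | 2.45 | 0.734 | 22.7% | 22.6% | 77% |
| 0.68 | 4.12 | 2.00 | 0.640 | 29.2% | 29.9% | 71% |
| 0.82 | 4.53 | 1.50 | 0.549 | 36.7% | 38.2% | 63% |

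Simulations used 78 + 39 patients and 10,000 trials per setting for f up to 0.52, and 68 + 34 patients and 2,000 trials for the last two rows. The random-slope analysis gave 9.2–10.6% across all settings simulated. With stratum in the model and 15% monotone dropout, REML fits at f = 0.46 gave 21.2% for the random intercept and 9.7% for random intercept plus slope.

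**A rough calibration.** Protocol 1.2 gives Day 57 SDs for 14 PRM-151 and 6 placebo patients.

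- Text: (13 × 3.8² + 5 × 3.0²)/18 = 12.93, SD 3.60
- Table 1-1: (13 × 4.0² + 5 × 3.3²)/18 = 14.58, SD 3.82
- s_b² = (25 − SD²)/(1 − (56/196)²) = 13.1 or 11.3, so f = 0.53 or 0.45
- Type I error: about 23% or 20%

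The 95% interval for the Day 57 SD is 2.7–5.3 (text) or 2.9–5.6 (table), which gives f anywhere from 0 to about 0.77. A patient-specific shift before Week 4 would also move the answer. With noise SD 3, a shift variance of 2, 4 or 7 taken out of the slope variance gives 14.1%, 12.6% or 10.0%. If the shift (variance 2–6) replaces noise instead, the result is 22–26%.

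**Other readings of the contrast.** SAP 5.3.1 says the mixed models "are all adjusted for baseline measurements of the response variable and stratification levels", although 5.2.5.1 lists no baseline covariate. With baseline as covariate and the Week 28 level contrasted, simulated error is 9.6% at f = 0, then 15.8%, 18.2%, 22.4% and 27.8% at f = 0.28, 0.50, 0.68 and 0.82. Refitting with categorical time still gives about 16% at f = 0.46.

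**The case against.** **The size is not known.** The calibration subtracts a Phase 1 SD, from mixed doses and another schedule, from a planning assumption of 5. If the Week 28 SD were 4 instead (an assumption), the same calculation gives f = 0.10–0.21 and an error of 12–14%. This stands: the 20–23% figure is an indication, and only the conditional table is firm.

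**The contrast is not fully specified.** SAP 5.2.5.1 and 5.3.1 disagree on the baseline covariate, and the ESTIMATE coefficients are not given. An unadjusted Week 28 level difference would stay near 10% (9.3–11.5%, or up to 12.3% with dropout). But that is not a change from baseline, and its power would be only 26–28%. Both readings that do give a change from baseline are inflated.

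**The SAP has other analyses without this fault.** EO1 reports the random-slope result, the multiple-imputation ANOVA does not depend on this covariance, and SAP 5.3.6 promises to explore and discuss substantial differences between the initially planned and primary analyses. The protocol also disclaims formal proof of superiority, and with complete balanced data the point estimate is unaffected. All of this is true, and it means a discrepancy would be seen. It does not repair the primary CI and p-value, from which the conclusions are drawn.

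**A random slope cannot be fitted everywhere.** HRCT and DLCO have one post-baseline value by Week 28, yet SO1, SO3 and SO8 refer to the primary model. This is correct and limits where the fix should go. Even the present random intercept is not identifiable with one outcome value per patient.

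**Conclusion.** The concern holds. The primary model gives the stated 10% error and 90% coverage at zero slope variance and is anti-conservative beyond that. The inflation is small if slopes explain up to 10% of the change variance (about 12%), about 15% at one quarter, and 20–23% at the rough Phase 1 calibration.

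These figures assume the planning SD of 5, linear individual trajectories and independent visit noise. Zero slope variance is necessary but not sufficient for validity, since serial correlation within patients would also break the random-intercept covariance. The mechanism is certain; the size in this trial is not. The SAP itself expects individual variability in EO1, so relying on zero slope variance in the deciding analysis is hard to justify. This should be fixed.

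**What to change.** In SAP 5.2.5.1, specify a random intercept and a random slope for time, with an unstructured 2 × 2 covariance, REML and Kenward-Roger degrees of freedom. This makes the EO1 model the primary analysis. Name an empirical (sandwich) variance as the fallback if the model does not converge.

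Carry the change to the repeated-measure analyses that reuse the model: SO2, SO7 and the patient-reported outcomes. Exclude SO1, SO3 and SO8. In the small no-therapy stratum of SO2, give the fallback a small-sample correction: with 20 + 10 patients and a t reference on 28 df, the uncorrected version runs at 12.0%.

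As a companion edit, state the exact contrast and reconcile 5.2.5.1 with 5.3.1 on the baseline covariate.

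The cost is two extra covariance parameters, a sentence on the fallback, and a wider interval. At f = 0.46 with 68 + 34 patients, the true per-patient variance is 23.31. The SE is √(23.31 × (1/68 + 1/34)) = 1.014 and the 90% half-width is 1.67 points, against the 1.28 that the present model would report. Power for 2.625 is Φ(2.625/1.014 − 1.645) = 82.7%, so the sample size need not change.

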5.2.5.2 Secondary efficacy analyses

For all secondary efficacy endpoints, the analyses will be based on observed data only *i.e.*, no data will be imputed. All the following analyses will be performed on both the ATS and the PP analysis data set.

SO1: *To determine the effect size of PRM-151 relative to placebo in change from Baseline to Week 28 in normal lung parenchyma (normal + mild LAA) and interstitial lung abnormalities (ILA) as quantified on high-resolution CT (HRCT) imaging analysis, pooling subjects on a stable dose of pirfenidone or nintedanib with subjects not on other treatment for IPF.*

HRCT is performed at baseline and W28. Descriptive statistics will be computed by treatment group for baseline, week 28 and change from baseline to Week 28 in total lung volume and volume (in ml and % of total lung volume) of parenchyma features representative of normal lung (normal + mild LAA) and representative of interstitial lung abnormalities (ILA) as quantified by HRCT imaging (see section 8, Statistical table 14.2.6.1.1 and 14.2.6.2.2). A model similar to that of the primary analysis (see section 5.2.5.1) will be used to compare the two groups (Statistical tables 14.2.6.3.1 to 14.2.6.3.2, Figure 14.2.4.1 to 14.2.4.2). Individual's measurement of total lung volume and volume of parenchymal features quantified by HRCT imaging will be reported in Listing 16.2.6.3.

SO2: *To determine the effect size of PRM-151 relative to placebo in change from Baseline to Week 28 in mean FVC% predicted, separately in subjects on a stable dose of pirfenidone or nintedanib and in subjects not on other treatments for IPF.*

The same model as the one for the primary analysis (see section 5.2.5.1) will be used for each subgroup (Statistical table 14.2.7.1.1 to 14.2.7.2.2, Figure 14.2.5.1.1 to 14.2.5.2.2). All measurements of FVC [% predicted] will be reported in Listing 16.2.6.1.1.

SO3: *To determine the effect size of PRM-151 relative to placebo in change from Baseline to Week 28 in normal lung (defined as normal + mild LAA) parenchyma and interstitial lung abnormalities (ILA) as quantified on HRCT imaging analysis, separately in subjects on a stable dose of pirfenidone or nintedanib and in subjects not on other treatments for IPF.*

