6.1 Change in the primary efficacy analysis

According to the protocol, the primary efficacy analysis was to be the Full Analysis Set (FAS), defined as all randomized patients having received at least one administration of the study medication with a baseline and at least one post-baseline assessment of FVC [% predicted] (primary efficacy criterion) available.

Limiting the population to subjects having at least one post-baseline assessment of FVC [% predicted] draws the efficacy population further from the intention to treat paradigm than the exclusion of only untreated patients. Consequently, it has been decided to change the primary efficacy analysis population to the All Treated Set (ATS, see section 3.2) defined as all randomized subjects who have received at least one administration of the investigational medicinal product (IMP).

In addition to this change of population, it has been decided to change the analysis model from the initially planned ANOVA model on change from baseline to week 28 to a linear mixed effect model with random intercept using all measurements available until Week 28 used to compute the estimate of the between group difference in change from baseline at week 28.

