9.1 List of tables

n°	Demographics and Baseline
14.1.1 to 14.1.3	Demographics (11.2)
14.1.2	Vital Signs at baseline
14.1.3	Physical examination at baseline
14.1.4	Hematology at baseline
14.1.5	Hematology abnormalities at baseline
14.1.6	Chemistry at baseline
14.1.7	Chemistry abnormalities at baseline
14.1.8	Coagulation at baseline
14.1.9	Coagulation abnormalities at baseline
14.1.10	Background therapy - use of nintedanib and pirfenidone prior to baseline
14.1.11.1.1 to 14.1.11.1.2	K-BILD Questionnaires at baseline
14.1.11.2.1 to 14.1.11.2.2	Leicester Cough Questionnaires at baseline
14.1.12.1 to 14.1.12.2	High Resolution Computed Tomography at Baseline
14.1.13.1 to 14.1.13.2	Pulmonary Function Tests at baseline
14.1.14.1 to 14.1.14.2	Six-minutes Walk Test at baseline
14.1.15.1 to 14.1.15.2	Pentraxin-2 levels at baseline
14.1.16.1 to 14.1.16.3	Anti-Pentraxin 2 antibodies (ADA) at baseline
14.1.17.1 to 14.1.17.3	Baseline Genetic Status
14.1.18.1 to 14.1.18.3	Biomarker levels at baseline
14.1.19	Disposition of patients (10.1)
14.1.20	Datasets analyzed (11.1)
14.1.21	Reasons for exclusion from the ATS
14.1.22	Reasons for exclusion from the PP
14.1.23	Reasons for study discontinuations
14.1.24	Major protocol deviations (10.2)
14.1.25	Minor protocol deviations (10.2)
14.1.26.1 to 14.1.26.2	Past medical history
14.1.27.1 to 14.1.27.2	Current medical history

14.1.28.1 to 14.1.28.2	Previous therapy for IPF
14.1.29.1 to 14.1.29.2	Current therapy for IPF
14.1.30.1 to 14.1.30.2	Previous other therapy
14.1.31.1 to 14.1.31.2	Current other therapy
14.1.32.1 to 14.1.32.2	Treatment compliance (11.3)
n°	Efficacy Results
14.2.1.1.1 to 14.2.1.1.3	(PO1) Forced Vital Capacity (% predicted FVC) - raw values at each visit
14.2.1.2.1 to 14.2.1.2.3	(PO1) Forced Vital Capacity (% predicted FVC) - change from baseline to each visit
14.2.1.3.1.a to 14.2.1.3.3.a	(PO1) Forced Vital Capacity (% predicted FVC): Anova table
14.2.1.3.1.b to 14.2.1.3.3.b	(PO1) Forced Vital Capacity (% predicted FVC): Model parameter estimates
14.2.1.3.1.c to 14.2.1.3.3.c	(PO1) Forced Vital Capacity (% predicted FVC): Least Square Means by stratum at each visit
14.2.1.3.1.d to 14.2.1.3.3.d	(PO1) Forced Vital Capacity (% predicted FVC): Least Square Means for Change from baseline at each visit
14.2.2.1.a	(PO1) Sensitivity Analysis: Forced Vital Capacity (% predicted FVC) - raw values by visit and stratum - No Background Therapy

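### As written, the primary model omits observed baseline FVC, so its Week 28 change from baseline rests on extending a straight line from Weeks 4-28 back to Day 0

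*SAP*

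**What the plan says.** SAP 5.2.5.1 specifies a random-intercept linear mixed model. The outcome is "raw values at each time point (from Week 4 to Week 28 included) in FVC [% predicted] as dependent variable (outcome", and the explanatory variables are stratum, treatment, time as actual days since baseline, and treatment by time. The treatment comparison is an ESTIMATE statement "of the between group difference in change from baseline at week 28", with no coefficients given. The table list in SAP 9.1 confirms that a change is meant: the primary-analysis tables include "Least Square Means for Change from baseline at each visit".

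Other sections describe the model differently.

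- SAP 5.3.1 says that pooled linear mixed models of variation over time "are all adjusted for baseline measurements of the response variable and stratification levels".
- SAP 5.1.2 allows any model with a time effect to be re-fitted, after a look at the residuals, with time "as a categorical variable (8 modalities) in order to explore non-linear trend in response variable". Weeks 4 to 28 give seven visits.
- SAP 6.1 describes a model "with random intercept using all measurements available until Week 28", without the Week 4 start.

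The model is also carried over to imaging and diffusion capacity. Under SO1 in SAP 5.2.5.2, "HRCT is performed at baseline and W28", and then "A model similar to that of the primary analysis (see section 5.2.5.1) will be used to compare the two groups"; SAP 6.2 calls it the same model. SO8 applies the primary model to DLCO, which Protocol 7.10.1 schedules before Week 28 only at Screening and Baseline.

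The originally planned ANOVA on change to Week 28 is kept, with multiple imputation, as a sensitivity analysis.

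**The concern.** A model that never sees the baseline value can give a change from baseline only by predicting baseline from its own fitted line. Under 5.2.5.1 that prediction lies four weeks before the first data point. The answer is right if the treatment effect grows linearly from Day 0, and generally wrong if it comes early, levels off or starts late.

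This matters because SAP 5.1.2 draws the efficacy conclusions from this single analysis, and the stated aim is a reliable estimate of effect size. The assumption about the shape over time is not stated, although the baseline measurement that would remove it is collected.

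The sponsor's own data do not make linearity safe. In the earlier multiple-dose study (Protocol 1.2, Table 1-1) the mean changes at Day 57 were +2.4 on PRM-151 and -1.5 on placebo. That is a difference of 3.9 at about Week 8, already above the 2.625 planned here for Week 28. The study was small (14 against 6) and used a different schedule, so it does not establish a plateau.

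**Working it through.** **1. The plan's own figure (SAP 2.3.2).** The placebo mean is 0.75 × (-1.5) + 0.25 × (-3) = -1.875, so the difference is 0.75 - (-1.875) = 2.625. With SD 5 and 68 against 34 patients, SE = 5 × √(1/68 + 1/34) = 1.05. Power at two-sided 0.10 is Φ(2.625/1.05 - 1.645) = 80%. The 102 evaluable patients reproduce, for an ANOVA on observed change. That ANOVA targets 2.625 whatever the shape of the effect before Week 28.

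**2. The contrast in 5.2.5.1.** Visits fall on days 28, 56, ..., 196, with mean 112 and Sxx = Σ(t - 112)² = 21,952. For a treatment effect d(t) and complete data, the contrast has expectation

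S = 196 × Σ(t - 112)d(t) / 21,952 = 0.25 × Σ(k - 4)d_k, with k = 1 to 7.

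If slopes are equal within arm and the SD of change is 5, the residual variance is 25/2 = 12.5. Then SE = 196 × √(12.5/21,952 × (1/68 + 1/34)) = 0.98.

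**3. Other readings.**

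- *Baseline as a Day 0 outcome* (eight time points, Sxx 32,928): (1/6) × Σ(k - 3.5)d_k with k = 0 to 7, SE 0.80.
- *Baseline as a covariate, linear time, read at Day 196*: mean of d_k + (84/196) × S. Assume a baseline SD of 11 (a uniform spread over the 50-90% entry range has SD 11.5). The between-patient variance given baseline is 108.5 × 12.5/121 = 11.2, so SE = √{[11.2 + 12.5 × (1/7 + 84²/21,952)] × (1/68 + 1/34)} = 0.87.
- *Baseline as a covariate, visit as a 7-level factor, read at Week 28*: d_7 = 2.625 for any shape, SE = √{(11.2 + 12.5) × (1/68 + 1/34)} = 1.02.

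The shapes below are illustrative; the documents give none. The true Week 28 difference is 2.625 in every row.

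| Shape of effect | 5.2.5.1 as written | Power | Baseline as outcome | Baseline covariate, linear time, Day 196 |
|---|---|---|---|---|
| Linear from Day 0 | 2.63 | 85% | 2.63 | 2.63 |
| Linear to Week 12, then flat | 1.75 | 55% | 2.48 | 3.00 |
| Linear to Week 8, then flat | 0.98 | 26% | 2.08 | 2.86 |
| Full by Week 4 | 0.00 | 10% | 1.53 | 2.63 |
| None until Week 8, then linear | 3.28 | 95% | 2.84 | 2.53 |

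For full effect by Week 4, Σ(k - 4) = 0, so the contrast is zero and its power equals alpha.

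**4. Adding baseline is not enough alone.** With complete data a baseline main effect is constant within patient and orthogonal to within-patient time. It leaves the treatment by time coefficient, and so S, unchanged. The contrast must also be read at Week 28.

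**5. The other contrast available without baseline.** Treatment plus 196 × interaction is a raw level difference at Week 28, not a change. Its SE is 1.75 to 3.19, with power 44% down to 21%, for an assumed between-patient SD of 8 to 15.

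**6. HRCT and DLCO.** With Week 28 as the only outcome time, slopes are not estimable at nominal Day 196, and the random intercept cannot be separated from residual error. If actual days spread evenly over the ±3-day window (SD 2 days), the SE of slope × 196 is 196 × √(1/68 + 1/34)/2 = 20.6 outcome SDs. A plain Week 28 comparison has SE √(1/68 + 1/34) = 0.21 SD.

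**The case against.** The best reply is that 5.3.1 governs. The primary model is a pooled mixed model of variation over time, and 5.3.1 says such models are baseline-adjusted. The protocol's over-time model (8.5.1.3.2) also has baseline as a covariate, and 5.1.2 and 6.1 can both be read as keeping baseline in. No section says that the ESTIMATE statement leaves out the treatment term. On that reading, with linear time read at Day 196, the estimates run from 2.53 to 3.00 (-4% to +14%) with power of about 90-96%, and most of the problem disappears. In addition, the observed-change ANOVA is retained and change by visit is tabulated by arm, so a distorted primary estimate would be visible.

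Parts of this stand. The extrapolation is inferred, because the coefficients are not given. Section 6.1 is loose wording rather than a contradiction. The re-fit rule in 5.1.2 follows a sentence on exploratory analyses, although it refers to all models with a time effect. The planned HRCT and DLCO model tables report least-squares means of change without reference to each visit, which hints that something other than a slope fit was in mind.

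It does not remove the point. Section 5.2.5.1 is the operative specification; it lists its variables and its outcome window, and baseline is in neither. The baseline covariate in 5.3.1 leaves the slope contrast unchanged, so 5.3.1 repairs the analysis only if the contrast is also read at Week 28, which the SAP does not say. A sensitivity analysis does not replace a distorted primary result. For HRCT, 6.2 calls for the same model, as SO8 does for DLCO.

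**Conclusion.** The concern holds. As written, the primary analysis does not use the observed baseline, and its contrast equals the planned 2.625 only under particular effect shapes, such as linear growth from Day 0. In the shapes examined it ranges from 0.00 to 3.28, and power from 10% to 95%, against 80% for the change-score ANOVA throughout. If the full effect is present by Week 4, three readings of the SAP give 0.00 (5.2.5.1), 1.53 (baseline as outcome) and 2.63 (5.3.1, read at Week 28).

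The sizes assume complete data from 68 and 34 patients, SD of change 5, equal slopes within arm, and illustrative shapes. They do not show that the wrong model will be run, and the stated sample size is not at fault. The primary model and contrast must be corrected before database lock.

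**What to change.** - In 5.2.5.1, add baseline FVC % predicted as a covariate, as 5.3.1 already states. Define the primary contrast as the baseline-adjusted treatment difference at Week 28, and write out the ESTIMATE coefficients.
- Preferably use visit as a 7-level factor with treatment by visit (treatment 1 -1 plus treatment by visit 1 -1 at Week 28). Linear time with baseline adjustment still returns 2.86 and 3.00 for the Week 8 and Week 12 plateaus. This is a preference with a price: SE about 1.02 against 0.87.
- Align 5.1.2, 5.3.1 and 6.1 with that model, and exclude the primary analysis from the residual-triggered re-fit.
- For HRCT and DLCO, use a Week 28 model with treatment, stratum and the baseline value.

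The cost is SAP wording before database lock. Baseline FVC, HRCT and DLCO are already collected, and 5.4.1 already replaces a missing Day 1 value with the last screening value. The visit-factor version needs assignment to nominal visits, which fits within the blind review of visit dates in 5.4.4.
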